#### **4.2.9 Accounting for the COVID-19 pandemic effects**

This study started during the severe acute respiratory syndrome coronavirus 2 (SARSCoV2)/Coronavirus disease 2019 (COVID19) pandemic, confirmed on 12th March 2020. The CSR will report how COVID-19 affected participants and/or study progression. COVID-19 assessments were carried out prior to the first IP administration and throughout the study and affected participants will be summarised.

A table will be produced to summarise any COVID-19 related study disruptions. The participant disposition table will incorporate COVID-19 as a further reason for discontinuing

study treatment. Participants affected by COVID-19 will be listed as well as those reported as having issues due to the COVID-19 pandemic in CTMS.

## 5 INTERIM ANALYSES

This section of the SAP is dedicated to the interim analyses (IA). Additional separate stand-alone SAPs were created for the Data and Safety Monitoring Board (DSMB) analyses as well as the Interim analyses.

The study incorporates two interim analyses:

- Futility analysis (IA 1):
  - When approximately 25% of participants are evaluable for the primary endpoint
  - The likely success of the study outcome will be assessed.
  - This analysis will enable the sponsor to make a go/no-go decision regarding continuation of the study as described by Frewer P. et. al., 2016. That is, the primary endpoint and WOMAC pain subscale endpoint will be analysed by most appropriate candidate model as specified in section 4.2.1.2.1.1 from which the pairwise model-based estimates versus placebo will be used for decision making purposes as follows:
    - Consider stopping the study if the lower limit of 1-sided 90% confidence interval for delta (MEDI7352 dose - Placebo) of change from baseline is below minus 1.5 (the target value).
    - Consider initiate planning for phase 3 if upper limit of 1-sided 80% confidence interval for delta (MEDI7352 dose - Placebo) of change from baseline is below minus 0.8 (the lower reference value).
  - Primary endpoint would be the main determinant of go/no go decision. If the primary endpoint is in the consider zone, then WOMAC pain subscale endpoint may help to determine the final decision.
  - This analysis will include disposition, baseline characteristics, primary efficacy, and key secondary efficacy (supportive) endpoint, which is change in the WOMAC pain subscale from baseline to Week 12.
- Interim analysis (IA 2):
  - When approximately 50% of participants are evaluable for the primary endpoint
  - This analysis will enable the sponsor to plan future project-related activities (without making any changes to the current study). At minimum, the same analyses as described for IA 1 will be performed. The decision making will proceed as follows:

- Consider initiate planning for phase 3 if upper limit of 1-sided 80% confidence interval for delta (MEDI7352 dose - Placebo) of change from baseline is below minus 0.8 (the lower reference value).
- This analysis will include the same evaluations as covered by the first interim analysis plus additional outputs as specified within this version of the IA SAP v2.0 and accompanying table shells. The interim analyses will be prepared by the blinded IQVIA biostatistics team. The unblinding of the interim analyses will be done by an independent unblinded IQVIA biostatistics team. The unblinded IQVIA biostatistics team will provide the unblinded interim analyses output to the Independent Efficacy Review Group (IERG).

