##### 3.1.3 Change and percentage change from baseline

In general, change from baseline outcome variables are computed as:

(post-baseline value - baseline value)

In general, percent change from baseline outcome variables are computed as:

$((\text{post-baseline value} - \text{baseline value}) / (\text{baseline value})) * 100$

However, for the primary endpoint, the change from baseline is defined as the weekly average of the daily NRS pain scores at Week x minus the baseline weekly average NRS pain score. The derivation of the weekly average of the daily NRS pain scores at Week x is described in section 3.2. In addition, for primary and key secondary endpoints the percent change from baseline is expressed in terms of improvement as follows:

$((\text{baseline value} - \text{Week 12 value}) / (\text{baseline value})) * 100$

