### **3.2 Primary efficacy variables**

The primary efficacy variable is the change in weekly average of daily NRS pain scores from baseline to Week 12.

The NRS is an 11-point Likert scale used to assess pain, where participants are asked to describe their average pain in the target knee by identifying a number from 0 = “no pain” to 10 = “most severe pain imaginable over the previous 24 hours”. This will be recorded on a daily basis at approximately the same time every morning. The daily NRS pain scores will be recorded via electronic patient recorded outcome (ePRO) diary.

The relevant visit associated with the daily NRS scores will be derived based on the date of NRS pain scores that coincide with the relevant visit date as recorded on the electronic case report form (eCRF). Therefore, the Week 12 weekly average of daily NRS pain scores is the average of the daily NRS pain scores of 7 days up to and including the date on which the week 12 (EOT/ET) visit occurred.

For participants that discontinue the treatment period, the date of the ET visit as recorded on the eCRF in form of the week 12 (EOT/ET) visit will be associated with the protocol defined visit based on the study day, and the 7-day average for that specific visit will be derived using the same approach as described above for the Week 12 average. If the ET visit coincides with the target study day of the EOT visit, then this ET average will not be derived as it cannot represent a valid Week 12 average. In other words, only participants that complete the treatment will have Week 12 average derived. For those who prematurely withdraw from the treatment the Week 12 average will be imputed. At least four of the seven daily scores need to be recorded by the participant to obtain a weekly average value including baseline for the statistical analyses.

If there are less than four daily scores for the Week 12 average due to an inappropriate visiting schedule of Week 11 (Week 11 and Week 12 in close succession), the derivation of the Week 12 average will take priority over the Week 11 average. The weekly average will be derived in the same manner as described above but daily scores that may have been used for derivation of the Week 11 average would instead be used for derivation of the Week 12 average to ensure that at least 4 scores are available.

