#### **4.2.1.2.1.2 Secondary analysis of the primary endpoint**

As a secondary analysis, pairwise testing will be performed as described in section 4. The same ANCOVA model used for the MCP-Mod procedure will be used on singly and multiply imputed data as specified in section 4.1.1.1 and results including the 80% upper and 90% lower 1-sided confidence intervals as well as 95% CIs and nominal p-values tabulated.

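### The IA 1 futility rule is reversed: it flags stopping when the target effect is still possible, not when it has been ruled out

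*SAP*

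**What the plan says.** SAP section 5 gives two decision rules for IA 1, the futility analysis at about 25% of participants evaluable. Both use "delta (MEDI7352 dose - Placebo) of change from baseline".

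- **Stopping rule:** "Consider stopping the study if the lower limit of 1-sided 90% confidence interval for delta" "of change from baseline is below minus 1.5 (the target value").
- **Phase 3 planning rule:** "Consider initiate planning for phase 3 if upper limit of 1-sided 80% confidence interval for delta" "of change from baseline is below minus 0.8 (the lower reference value").

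The planning rule is repeated for IA 2; the stopping rule is not. Section 5 also expects a middle zone between go and no-go, in which WOMAC pain may inform the decision.

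Two definitions fix the sign. Section 3.1.3 defines change for the primary endpoint as "the weekly average of the daily NRS pain scores at Week x minus the baseline weekly average NRS pain score". Section 3.2 has participants "describe their average pain in the target knee by identifying a number from 0" for no pain up to 10 for the worst pain. Section 4.2.1.2.1.1, Step 5, treats 1.5 points as an improvement over placebo.

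Section 4.2.1.2.1.2 tabulates "80% upper and 90% lower 1-sided confidence intervals" for the pairwise comparisons. This is the same pair of limits as in section 5, though it says nothing about the direction of any decision.

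**The concern.** With benefit negative, the lower 1-sided 90% limit is the optimistic end of the evidence. A futility rule built on it should fire when even that end falls short of minus 1.5, that is, when the limit lies above minus 1.5. The SAP says the opposite. A strongly positive result meets the stopping rule, and a result that excludes the target does not.

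This is the only futility criterion in the document, and it belongs to an unblinded go/no-go analysis. Applied literally, it points towards stopping when the drug works and towards continuing when it does not. It also overlaps with the planning rule beside it, so a single result can call for stopping the study and for planning phase 3.

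**Working it through.** The SAP gives no operating characteristics for IA 1, so there is no stated figure to reproduce. The check takes the rules as written and evaluates them under normal theory.

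**Inputs from the SAP**
- Delta is active minus placebo; target minus 1.5; lower reference value minus 0.8; IA 1 at about 25% evaluable (section 5).
- Five arms, equal allocation (section 1.2).
- Information equivalent to 255 completers, or about 350 randomised (section 1.3).

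**Assumptions**
- SD of the change score 1.5 to 3.0 (not in the SAP).
- Evaluable per arm: 0.25 × 255 / 5 = 12.75, or 0.25 × 350 / 5 = 17.5.
- Simple pairwise SE = SD × √(2/n). This runs from 1.5 × √(2/17.5) = 0.51 to 3.0 × √(2/12.75) = 1.19. The model-based estimates named in section 5 would generally have smaller SEs.

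**Thresholds for the point estimate**
- Stop as written: estimate − 1.2816 SE < −1.5, so estimate < −1.5 + 1.2816 SE.
- Stop with the inequality reversed: estimate > −1.5 + 1.2816 SE.
- Go: estimate + 0.8416 SE < −0.8, so estimate < −0.8 − 0.8416 SE.

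**Two single results, SE 0.5**
- Estimate −2.0: lower 90% limit −2.64, upper 80% limit −1.58. The written stopping rule and the planning rule both fire.
- Estimate 0.0: lower 90% limit −0.64. The target is excluded, yet the stopping rule does not fire.

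**Overlap.** Every go result is also a stop result when −0.8 − 0.8416 SE ≤ −1.5 + 1.2816 SE, that is 0.7 ≤ 2.123 SE, or SE ≥ 0.33. With 12.75 to 17.5 per arm, a simple pairwise SE below 0.33 would need an SD of about 1.0 or less. Smaller SEs do not cure the problem: an estimate of −2.0 with SE 0.2 gives limits of −2.26 and −1.83, and both rules fire.

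**Probability of flagging a stop**, P = Φ((−1.5 + 1.2816 SE − δ)/SE) as written, and 1 − P when reversed. Each cell shows written / reversed:

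| True δ | SE 0.51 (SD 1.5, n 17.5) | SE 0.68 (SD 2.0, n 17.5) | SE 1.19 (SD 3.0, n 12.75) |
|---|---|---|---|
| +0.5 | 0.4% / 99.6% | 4.7% / 95.3% | 34.4% / 65.6% |
| 0 | 4.7% / 95.3% | 17.4% / 82.6% | 50.8% / 49.2% |
| −1.5 | 90% / 10% | 90% / 10% | 90% / 10% |
| −2.0 | 98.8% / 1.2% | 97.8% / 2.2% | 95.6% / 4.4% |
| −2.5 | 99.9% / 0.1% | 99.7% / 0.3% | 98.3% / 1.7% |

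At δ = −1.5 the expression reduces to Φ(1.2816) = 0.90, so that row does not depend on SE.

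**Middle zone.** As written with SE above 0.33, the only results that trigger neither rule are the poor ones, with estimates above −1.5 + 1.2816 SE. Reversed, the results that trigger neither lie between the go and stop thresholds. At SE 0.68 that is between −1.37 and −0.63, which is the middle zone section 5 describes.

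**The case against.** The strongest objections concern consequence, not the error itself.

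- **Another document may govern.** Section 1 says this SAP covers the final analyses, and section 5 says stand-alone interim SAPs were created. Section 5 may be a faulty summary of a correct rule. This stands, and the SAP cannot settle it. Section 5 also refers to itself as a version of the interim SAP, which suggests copied text, so the error could be in both places.
- **Timing.** The amendment history is dated August to September 2023, before final lock, so both interims were probably complete. The documents give no interim dates. If this is right, the correction changes no IA 1 decision, but it still matters for the record and for confirming what was applied.
- **The rule is advisory.** It says to consider stopping, the unblinded output goes to an independent review group, and a reader who saw both rules fire would probably notice. This limits the harm but does not make the sentence right.
- **The probabilities are illustrative.** The SD is assumed, the SE is not the model-based one, and one dose is considered where four are compared. This stands for every row of the table except δ = −1.5.

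No alternative reading rescues the wording. Taking *below* to mean smaller in magnitude would repair the stopping rule but break the planning rule, which uses the same word and the same delta. The improvement-signed formula in section 3.1.3 applies to percent change, which these rules do not use.

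**Conclusion.** The concern holds. The IA 1 stopping rule in SAP section 5 is stated in the wrong direction and conflicts with the correctly stated planning rule beside it. The conclusion rests only on the SAP's own definitions of delta, change and scale. For a single pairwise comparison under normal theory, a true effect at the target is flagged for stopping 90% of the time instead of 10%, whatever the SE. The size of the error at other true effects, and the claim that the overlap covers every go result at IA 1, rest on the assumed SD and sample size. Whether any decision was affected depends on the interim SAP and programs, which are not available here.

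**What to change.** In SAP section 5, under IA 1, change the stopping rule to: consider stopping if the lower limit of the 1-sided 90% confidence interval for delta is **above** minus 1.5. Leave the planning rule unchanged. The limit itself needs no change, since section 4.2.1.2.1.2 also pairs a lower 90% with an upper 80% limit.

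Then check the stand-alone interim SAP, its table shells and the programs for the same direction. If IA 1 has been run, record which direction was programmed and applied. The cost is one word in this SAP and a short document and program check; no design, sample size or final analysis changes.

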## 6 CHANGES OF ANALYSIS FROM PROTOCOL

- The final analysis and its reporting will be split to two deliverables that would be supported by two database locks at timepoints specified in section 1. This is to evaluate the efficacy data once all participants complete the treatment period as it is not anticipated that this data will change rather than waiting once all participants complete the study especially after the follow-up period was extended from 12 to 24 weeks.
- Single imputation will be performed only for the primary and key secondary endpoints as it is not meaningful to perform the single imputation for endpoints that will only be summarised.
- The sequentially rejective multiple comparison approach includes not just pairwise comparisons, but also the dose response curve for the WOMAC pain subscale score. In addition, MCP-MOD analyses of the remaining key secondary endpoints will not be performed.
- Additional supplementary analyses not specified in the protocol were added for comparative purposes within the industry. Those are: ANCOVA analysis of the primary endpoint and WOMAC pain subscale score key secondary endpoint using singly imputed LOCF cases as well as ANCOVA analysis of the WOMAC pain subscale score key secondary endpoint using multiply imputed cases that were imputed using the sampling from normal distribution approach.
- The protocol presents the concomitant medication and therapies as a safety endpoint. However, this data does not necessarily evaluate the safety and hence was moved as part of participant disposition which is in alignment with AZ standard shells reporting.
- CCI [REDACTED].
- The definition of the treatment emergent AEs was clarified to account for instances where a participant withdraws from the study over a phone call and disposition (DS) page in eCRF is populated without the corresponding visit being recorded. In addition, the change in relationship was removed as pre-treatment AE that changes the relationship would need to be entered in the database as a new AE with a start date on or after the first IP administration date and hence would automatically become a treatment emergent AE as per the first part of the definition.
- Other secondary endpoints, DSIS and rescue medication use will be summarised and analysed using available data on protocol specified visits and not just those visits specified in the definition of the endpoint itself (Week 2, 4, 6, 8, 10, 12 and 18).
- Provided that the ECG evaluations are performed locally by sites, only the abnormal evaluations will be listed.
- Given that TNSn and Injection site reactions data are tabulated, the listings were not generated.

- An additional AESI category was defined in this SAP that does not feature in the protocol. This category was classed as ‘Other AESIs’ and has been defined as any other AEs that are deemed of an interest by the study team.

## 8 APPENDICES

### Appendix A Questionnaires derivations

#### Appendix A1 WPAI:OA

The table below summarize the six questions of the WPAI:OA questionnaire, and the derivations of the four endpoints of the effect of impairment on activity and impairment.

Question	Question Wording	Scoring
1	Are you currently employed? [if No skip to question 6]	Yes, No
2	During the past seven days, how many hours did you miss from work due to problems associated with your OA of the knee or hip?	number of hours (free text)
3	During the past seven days, how many hours did you miss from work because of any other reason, such as vacation, holidays, time off to participate in this study?	number of hours (free text)
4	During the past seven days, how many hours did you actually work? (if '0' skip to Question 6)	number of hours (free text)
5	During the past seven days, how much did your OA of the knee or hip affect productivity while you were working?	0 to 10 scale with 0 being 'No effect on my work' and 10 being 'Completely prevented me from working'
6	During the past seven days, how much did your OA of the knee or hip affect your ability to do your regular daily activities, other than work at a job?	0 to 10 scale with 0 being 'No effect on my daily activities' and 10 being 'Completely prevented me from doing my daily activities'

WPAI endpoint	Calculation
---------------	-------------

Percent activity impairment due to Osteoarthritis	$Q6 * 10$
Percent impairment while working due to osteoarthritis	$Q5 * 10$
Percent overall work impairment due to osteoarthritis	$\left\{ \frac{Q2}{Q2+Q4} + \left[ 1 - \left( \frac{Q2}{Q2+Q4} \right) \right] \left( \frac{Q5}{10} \right) \right\} * 100$
Percent work time missed due to Osteoarthritis	$\frac{Q2}{Q2 + Q4} * 100$

### Appendix A2 Responses and scores of the HCRU questionnaire

Question	Response	Scoring

During the last X weeks what services did you receive directly related to your osteoarthritis?
 
 
• Primary Care Physician;
 
• Neurologist;
 
• Rheumatologist;
 
• Physician Assistant or Nurse Practitioner;
 
• Pain Specialist;
 
• Orthopaedist;
 
• Physical Therapist;
 
• Chiropractor;
 
• Alternative Medicine or Therapy (Concomitant Medications);
 
• Podiatrist;
 
• Nutritionist/Dietician;
 
• Radiologist;
 
• Home healthcare services;
 
• Other;
 
	Number of visits	Response not selected= 0 Number of visits= 1-999
During the past X weeks, have you visited the emergency room due to your osteoarthritis?	Yes, No	No = 0 Yes = 1
How many times?	Number of visits	0-999

During the past X weeks, have you been hospitalized due to your osteoarthritis?	Yes, No	No = 0 Yes = 1
How many nights in total did you stay in hospital due to your osteoarthritis in the last X weeks?	Number of Nights	0-999
Did you use these aids or devices to help you in doing things because of your osteoarthritis in the last X weeks?  
 
• Walking Aid
 
• Wheelchair
 
• Devices or utensils to help you dress, eat or bathe
 
• Other
 
	Did not use any aids or devices never, rarely, sometimes, often, always	Did not use any aids or devices= 0 Device not selected= 0 Never = 1 Rarely = 2 Sometimes = 3 Often = 4 Always = 5
Did you quit your job because of your osteoarthritis?	Yes, No	No = 0 Yes = 1 Not applicable = 2
How long ago did you quit your job because of your osteoarthritis?	Years and Months	0-99 Years and 0-99 Months (should be max of 11 months)

## **Appendix B Multiple Imputation**

### **Appendix B1 The pattern mixture framework**

The MAR imputation will be performed for all participants, regardless of the intercurrent event, on the observed and imputed data from step 1 (intermediate missing data imputation), including the imputed baseline from step 0 also. The same will be performed for MNAR approach. This would result in two sets of multiply imputed datasets: one set under MAR assumption and one set under MNAR assumption.

The final set that would then be used for further analysis will be compiled such that only imputed data from either MAR or MNAR sets would be selected based on the participants' intercurrent event. For example, if a participant discontinues treatment due to an adverse event, then only data from the MNAR set would be included in the final set, whilst data of a participant who discontinues treatment due to their decision would come from only MAR set.

### **Appendix B2 The sampling from normal distribution approach**

1. Obtain the standard deviation from observed WOMAC pain subscale scores at Week 12 for all participants in FAS
2. Sampling from normal distribution to be executed using the following data step:  
rand('NORMAL' BASE,stddev) or rand('NORMAL',LOCF,stddev)
  - a. where the stddev is obtained in step 1
  - b. BASE or LOCF are either participant's baseline score or participant's last observed WOMAC pain subscale score.
3. Step 2 to be performed 100 times
4. Data to be ordered by ParticipantID and imputation to have the same seed number and produce identical results on production and QC

NOTE:

- No intermediate missing data imputation step is needed.
- For LOCF, consider available WOMAC pain subscale scores of all post-baseline visits (not just protocol defined visits), except unscheduled visits. That is, if participant has Week 11 WOMAC score, this score can be used as last observation for LOCF imputation.

## Appendix C MCP-Mod: Combining Estimates from Multiple Imputed Datasets

CCI

CCI

## Appendix DMCP-Mod Code

Referenced in SAP section [4.2.1.2.1.1](#)

### Appendix D1 Deriving optimum contrast coefficients

The below code alongside the combined dose estimates and covariance matrix derived in appendix B can be used to obtain the optimum contrast coefficients.

```
/*Specify doses*/

data doses;
  input dose @@;
  datalines;
    0 7.5 25 75 150;
  ;
run;

/*Specify candidate models*/

data models;
  length modnam $25;
  input modnam par1-par3;
  datalines;
    emax 10 . .
    emax 40 . .
    emax 80 . .
    linear . . .
    exponential 10 . .
    exponential 25 . .
  ;
run;

/*Write optimal contrasts in data set optcontrasts and in global macro variable modcontr */

%optcont(models=models, dose=doses, sigma=scalemat, direction=incr, dosevarname=dose);

proc print data optcontrasts label noobs;
  title "Optimal contrasts for defined models";
run;

%optcont macro code

%macro optcont(models=,doses=,sigma=,direction=,dosevarname=);

/*****
```

